13.1.1.1. Comparability of Historical Controls

Utilization of both historical control/observational databases (UK-PBC and Global PBC Study Group), with more than 6000 subjects each, allow for a rigorous subject level meta-analysis. The historical databases include long-term follow up, detailed subject-level information such as

baseline clinical characteristics, longitudinal liver biochemistry, and long-term outcomes, and span a broad range of subject characteristics that may influence disease (disease state, age, gender, and regional differences in standard of care). Historical controls from both databases will be chosen based on the same study inclusion/exclusion criteria where possible.

13.1.2. Determination of Sample Size

The following assumptions were used in sample size calculations:

- Exponential survival curves, placebo survival estimate of 0.5 at 8 years with a hazard ratio of 0.60, and total study duration of 8 years, allowing for 2 years accrual and 6 years of follow up.
- 5% of the subjects will have never been treated with UDCA; 95% of the subjects will have been on UDCA for at least 1 year.
- Subjects will be randomized in a 1:1 ratio to placebo or OCA.
- The 2 groups will be compared using a 2-sided log rank test at the 5% level of significance.

Based on the randomization ratio, significance level, and assumed hazard ratio, a total of 121 events (both groups combined) will provide 80% power to demonstrate a statistically significant difference between OCA and placebo on time to liver-related outcomes, including all-cause mortality.

In addition, based on the remaining assumptions stated above, it is estimated that approximately 350 subjects will be enrolled to attain 121 events.

13.1.2.1. Sample Size Re-Estimation Plan

Conducting a long-term outcomes study given the low disease prevalence, relatively slow disease progression, and ethical considerations, which in combination will impact recruitment and event rates, is inherently difficult. As stated in ICH E9, in long-term trials there is an opportunity to check the assumptions that underlay the original design and sample size calculations. The power stated above depends on the total number of events. Thus, the overall survival function can be estimated without unblinding.

Therefore, starting approximately 2 years after the first subject is randomized, the aggregate event rate and sample size based on recruitment and retention will be evaluated in a blinded manner quarterly. This evaluation will determine if any increases in number of subjects are required in order to obtain a total of 121 adjudicated events for the final analysis in the combined groups. Specifically, the pooled number of events will be available during the study in a blinded manner, without any knowledge of the comparative efficacy in the treatment groups. This method for evaluating the sample size does not inflate the type I error rate. Additional subjects may be enrolled as appropriate.

If after 4 years of accruing subjects, despite increases in the number of subjects, it is determined that at least an additional 2 years (ie, total study duration of at least 10 years) are needed to randomize sufficient subjects to achieve a total of 121 adjudicated events, all subjects enrolled from that point forward will receive open-label OCA. Previously randomized subjects will continue to be treated in a blinded manner with either OCA or matching placebo. If this

modification is implemented, the alternative primary efficacy analysis is specified in [Section 13.1.9](#).

Any revised sample size or changes to treatment allocation will be justified and documented in a protocol amendment and in the CSR.

13.1.3. Primary Efficacy Analysis

The primary efficacy endpoint will be the time to first occurrence of one of the following post-randomization:

- Death (all-cause)
- Liver transplant
- MELD score ≥ 15
- Hospitalization (as defined by a stay of 24 hours or greater) for new onset or recurrence of:
 - Variceal bleed
 - Encephalopathy (as defined by a West Haven score of ≥ 2)
 - Spontaneous bacterial peritonitis (confirmed by diagnostic paracentesis)
- Uncontrolled ascites (diuretic resistant ascites requiring therapeutic paracentesis at a frequency of at least twice in a month).
- Hepatocellular carcinoma confirmed by 2 complimentary imaging modalities.

The primary efficacy analysis will compare randomized OCA to randomized placebo with respect to the primary efficacy endpoint using the ITT population. Only adjudicated events will be included in analyses. The 2 treatment groups will be compared using the log rank test stratified by the randomization stratification factor. Kaplan-Meier (KM) estimates of the distribution of the time-to-event will be tabulated and graphed by treatment group. The tabulation will include the KM estimate of the medians and corresponding 95% confidence intervals (CIs), if the medians can be estimated. The number and percent of subjects censored and with events will be presented. The hazard ratio and 95% CI will be determined based on a Cox regression model stratified by randomization strata to estimate the magnitude of the effect.

13.1.4. Key Secondary Efficacy Analyses

The key secondary efficacy endpoints will compare OCA to placebo on the following:

- Time to first occurrence of MELD score ≥ 15
- Time to liver transplant or death (all-cause)
- Change from Baseline in total bilirubin at end of study
- Change from Baseline in ALP at end of study

The key secondary efficacy analyses will compare randomized OCA to randomized placebo in ITT population with respect to the key secondary efficacy endpoints. Only adjudicated events will be included in time-to-event analyses. The comparison (hypothesis testing) will be

conducted as specified in [Section 13.1.11](#) in a sequential closed testing gate-keeping procedure, provided that the primary efficacy endpoint comparison is statistically significant in favor of the OCA treatment group. If the primary comparison is not statistically significant then comparison of the secondary endpoints will be considered as descriptive and exploratory. This procedure controls the study-wise type I error.

The 2 treatment groups will be compared using the same methodology as specified for the primary efficacy analysis ([Section 13.1.3](#)).

Analyses of change from Baseline to end of study in ALP and total bilirubin will be compared between treatment groups using analysis of covariance (ANCOVA) with change from Baseline as the dependent variable including treatment group and randomization stratification factor as fixed effects and the Baseline values as a covariate. The same analysis will be carried out using percentage change from Baseline as the dependent variable.

Descriptive statistics of the laboratory values will be summarized by treatment group. The results, change from Baseline, and percentage change from Baseline values as well as estimates of least-square means, standard errors, and 95% CIs will be presented by treatment group. Estimates of the mean difference between treatment groups, the standard error of the difference, and 95% CI of the difference will be presented.

13.1.5. Additional Secondary Efficacy Analyses

The following time to event secondary efficacy analyses will compare randomized OCA versus randomized placebo using the ITT population:

- Time to each component of the primary efficacy endpoint (except MELD score ≥ 15 which is captured above)
- Time to development of varix/varices
- Time to liver-related death
- Time to liver-related death or liver transplant
- Time to liver-related death, liver transplant, or MELD score ≥ 15

The same analysis methodology as used for the primary efficacy analysis will be used for these secondary efficacy analyses. Similar endpoints, where available, will be analyzed to compare OCA to historical controls as described below in [Section 13.1.8](#).

Analyses of changes in liver biochemistry (GGT, ALT, AST, conjugated bilirubin, albumin, and INR) will be summarized and analyzed using the same methodology as specified in [Section 13.1.4](#) for the key secondary analyses of change in ALP and total bilirubin.

Analyses of changes in MELD score, Child-Pugh score, Mayo Risk Score (MRS), IgM, CRP, TNF- α , FGF-19, CK-18, C4, and ELF score will be summarized and analyzed using the Wilcoxon Rank Sum Test to compare treatment groups. The median differences and 95% CI of the median differences between treatment groups will be constructed using Hodges-Lehmann estimate. If the median differences between treatments are not symmetrical around the median, the Sign Test may be used.

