11.1.2. Secondary Assessments

The following secondary efficacy assessments will be measured:

- Liver-related death
- Liver biochemistry (see [Table 5](#) for list of analytes to be tested)
- Biomarkers, including markers of hepatic fibrosis and/or inflammation, to be tested will include: IgM, c-reactive protein (CRP), tumor necrosis factor- α (TNF- α), FGF-19, cytokeratin-18 (CK-18) and ELF, Fibroscan (and others as determined during the course of the study).
- Data will be collected to inform quality of life and cost-effectiveness analyses that are relevant to major health care systems around the world. Quality of life will be assessed by questionnaires (PBC-40, EQ-5D-5L, and FIS) administered annually. Resource utilization information will be collected from the Medical and Surgical Treatment Procedures and Office Visit Log or other CRFs such as number, type and duration of hospitalizations, number of outpatient physician visits (subject reported), and use of concomitant medications.
- Endoscopy will be conducted at selected study sites where the device is available to assess for the presence of oesophageal varix/varices at baseline. Throughout the study, any endoscopy performed as part of the annual study assessments or standard of care will be collected in the case report form to assess for the development of varix/varices.

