13.1. Efficacy Analysis

13.1.1. Analysis Populations

The following subject populations will be evaluated and used for presentation and analysis of the data:

- The Randomized Population will include all randomized subjects.
- The Intent-to-Treat (ITT) Population will include all randomized subjects who receive any amount of investigational product (OCA or placebo). The ITT Population will be the primary population used for efficacy analyses. Treatment assignment will be based on the randomized treatment.
- The Safety Population will include all subjects who received any amount of investigational product (placebo or OCA). The Safety Population will be the primary population used for safety analyses. Treatment assignment will be based on the treatment actually received.
- The PK population will include all OCA subjects who have at least one confirmed fasted analyzable sample. Subjects must have been fasting for approximately 8 hours prior to the visit and must not have any major protocol deviations that potentially affect exposure levels. The PK population will be used for OCA PK analyses.
- The Overall Historical Control Population will include subjects from the United Kingdom (UK) -PBC Group and Global PBC Study Group databases with demonstrated comparability to randomized subjects in this clinical study (747-302) with respect to both subject characteristics and disease progression.
- The UK-PBC Historical Control Population will include subjects from the UK-PBC Group databases with demonstrated comparability to randomized subjects in this clinical study (747-302) with respect to both subject characteristics and disease progression.
- The Global PBC Historical Control Population will include subjects from the Global PBC Study Group database with demonstrated comparability to randomized subjects in this clinical study (747-302) with respect to both subject characteristics and disease progression.

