 - Spontaneous bacterial peritonitis (confirmed by diagnostic paracentesis)
- Uncontrolled ascites (diuretic resistant ascites requiring therapeutic paracentesis at a frequency of at least twice in a month)
- Hepatocellular carcinoma confirmed by 2 complimentary imaging modalities

Every event for enrolled subjects will be adjudicated by an independent committee.

Primary Efficacy Analysis

The primary efficacy analysis will compare randomized OCA to randomized placebo with respect to the primary efficacy endpoint using the ITT population. The 2 treatment groups will be compared using the log rank test stratified by the randomization stratification factor. Kaplan-Meier (KM) estimates of the distribution of the time-to-event will be tabulated and graphed by treatment group. The tabulation will include the KM estimate of the medians and corresponding 95% confidence intervals (CIs), if the medians can be estimated. The number and percent of subjects censored and with events will be presented. The hazard ratio and 95% CI will be determined based on a Cox regression model stratified by randomization strata to estimate the magnitude of the effect.

Key Secondary Efficacy Analyses

The key secondary efficacy endpoints are as follows:

- Time to first occurrence of MELD score ≥ 15
- Time to liver transplant or death (all-cause)
- Change from Baseline in total bilirubin at end of study
- Change from Baseline in ALP at end of study

The key secondary efficacy analyses will compare randomized OCA to randomized placebo in ITT population with respect to the key secondary efficacy endpoints. Only adjudicated events will be included in time-to-event analyses. The comparison (hypothesis testing) will be conducted in a sequential closed testing gate-keeping procedure (in the order in which the key secondary endpoints are stated above), provided that the primary efficacy endpoint comparison is statistically significant in favor of the OCA treatment group. If the primary comparison is not statistically significant then comparison of the secondary endpoints will be considered as descriptive and exploratory.

Other Efficacy Analyses

The following secondary efficacy analyses will compare OCA to placebo on time to the following events:

- Each component of the primary efficacy endpoint (except MELD score ≥ 15 which is listed above)
- Development of varix/varices
- Liver-related death
- Liver-related death or liver transplant

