β-hCG = beta human chorionic gonadotropin; DEXA = dual-emission X-ray absorptiometry; EOS= End of Study; EOT = End of Treatment; FGF = fibroblast growth factor-19; FIS= Fatigue Impact Score; IP = Investigational Product; M = month, wk = week

^a All subjects will have the chemistry panel retested to ensure subjects have 2 ALP and bilirubin assessments at least 2 weeks apart to calculate the mean result for both analytes.

The mean of all screening ALP and bilirubin assessments will be used to determine eligibility. Samples for hematology and coagulation will not be collected at Screening Visit 2.

^b The subject should be contacted by telephone on a monthly basis in between at-clinic study visits at Month 1 and Month 2 (±1 week), and also 2 weeks post dose titration (up or down), to assess for AEs and concomitant medications and to verify that s/he is dosing as directed.

^c As soon as possible upon study discontinuation and as near as possible to last dose taken.

^d Visits should be based on Day 0 (not on the prior visit).

^e Medical history at Screening and the yearly physical exam will include an assessment of smoking and alcohol consumption history and current habits for both.

^f Height will be collected at this visit.

^g The EQ-5D-5L and FIS Quality of Life questionnaires are validated for use in multiple languages. If a validated translation is not available in the local language required for a specific study subject, the data from that questionnaire will not be collected (See Section 11.1.2.2 and Section 12.2.6).

^h Transient elastography (TE) will be conducted at selected study sites where the Fibroscan® TE device is available. Similarly, DEXA will be conducted at selected study sites where the DEXA device is available. Please refer to Section 9.7.4 for additional information related to the allowed windows at Day 0 for these specific procedures.

-
- ⁱ Endoscopy will be conducted at selected study sites where the device is available to assess for the presence of oesophageal varix/varices. Please refer to [Section 9.7.4](#) for additional information related to the allowed window at Day 0 for this specific procedure.
 - ^j Ultrasound will be conducted to enhance HCC surveillance. If a lesion is found, a second confirmatory image (eg, MRI) should be obtained. Please refer to [Section 9.7.4](#) for additional information related to the allowed windows at Day 0 for this specific procedure

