9.7.4. Day 0 Procedures (Randomization)

- Review inclusion and exclusion criteria for eligibility.
- Assess and record vital signs (weight, oral temperature, sitting heart rate, respiratory rate, and sitting blood pressure).
- Subject and Quality of Life questionnaires (see [Section 11.1.2.2](#) and [Section 12.2.6](#)).
- Perform transient elastography (TE; at selected study sites, where available) using the Fibroscan[®] TE device. If TE has been done within 6 months of Day 0 and a report/adequate data are available, a pretreatment TE at Day 0 is not required. If the TE cannot be performed on Day 0 (e.g., device/technician unavailability, scheduling issues, etc), the procedure may be completed within the screening visit window, as close as possible to the Day 0 visit, after subject eligibility has been confirmed.
- Conduct a DEXA bone density scan (at selected study sites, where available); document whether the subject stopped taking her/his calcium supplements for 48 hours before the scan and medications for osteoporosis or osteopenia on the day of the scan, if applicable. If DEXA has been done within 12 months of Day 0 and a report/adequate data are available, a pretreatment DEXA at Day 0 is not required. If the DEXA cannot be performed on Day 0 (e.g., device/technician unavailability, scheduling issues, etc), the procedure may be completed within the screening visit

window, as close as possible to the Day 0 visit, after subject eligibility has been confirmed.

- Perform an esophagogastroduodenoscopy (endoscopy; at selected study sites, where available) to assess the presence or absence of oesophageal varix/varices. If an endoscopy has been done within 12 months of Day 0 and a report/adequate data are available, a pretreatment endoscopy at Day 0 is not required. If the endoscopy cannot be performed on Day 0 (e.g., device/technician unavailability, scheduling issues, etc), the procedure may be completed within the screening visit window, as close as possible to the Day 0 visit, after subject eligibility has been confirmed.
 - Subsequent endoscopies should be performed annually or per standard of care and the Investigator's clinical judgment throughout the course of the study.
Endoscopies should also be performed when platelet counts are $<150 \times 10^9/L$.

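### Time to development of varices is analysed in the whole ITT population, which includes subjects who already have varices or whose baseline status is unknown

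*Protocol*

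**What the plan says.** Section 13.1.5 opens its list with "The following time to event secondary efficacy analyses will compare randomized OCA versus randomized placebo using the ITT population". The list includes "Time to development of varix/varices", and the section adds: "The same analysis methodology as used for the primary efficacy analysis will be used for these secondary efficacy analyses". Section 13.1.1 defines ITT as every randomized subject who took any study drug, with no condition on endoscopy. The Amendment 1.1 synopsis still lists "Development of varix/varices" with the same method. The available text of Amendment 1.1 stops before its Section 13, so the detailed wording cited here is that of Amendment 1.

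The rules on ascertainment are elsewhere:

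- **Baseline.** The schedule footnote in Section 7.1.2 says: "Endoscopy will be conducted at selected study sites where the device is available to assess for the presence of oesophageal varix/varices". Section 9.7.4 accepts a report up to 12 months old in place of a Day 0 examination.
- **On study.** Section 11.1.2 says that "any endoscopy performed as part of the annual study assessments or standard of care will be collected in the case report form" to assess development of varices. This is not limited to subjects who had a baseline endoscopy.
- **Eligibility.** Exclusion 2 in Section 8.3 names variceal bleeding, current or within 12 months. Varices that have not bled are not listed.
- **Censoring.** Section 13.1.10.1 censors subjects without an event at last contact.
- **Status.** Section 13.1.11 places endpoints outside the hierarchy on a descriptive and exploratory footing.

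**The concern.** Development of varices is an incident event. It can be observed only in a subject known to be free of varices at the start and examined again later. The ITT population adds three groups for whom that does not hold:

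1. **No baseline endoscopy, examined later.** Varices found at the first on-study examination cannot be told from varices present at entry, and nothing in the text says how to classify them.
2. **Varices on the baseline endoscopy.** These subjects stay in the risk set although they have nothing left to develop.
3. **Never examined.** They contribute event-free time up to last contact, although nobody looked.

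Group 1 matters most for the treatment comparison. Varices already present at randomization cannot be prevented by treatment and are balanced in expectation, so counting them as events pulls the hazard ratio towards 1. Groups 2 and 3 mainly lower the reported incidence.

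**Working it through.** **The plan's own figure.** The protocol states no event rate or power for this endpoint. Its only power figure is 121 primary-endpoint events for 80% power at a hazard ratio of 0.60, 2-sided 5%. Schoenfeld's formula reproduces it: 4 × (1.960 + 0.842)² / (ln 0.60)² = 120.3, rounded up to 121. It does not bear on varices, so the size of the problem has to be illustrated on assumptions.

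**Assumptions, not in the protocol.** Prevalence of varices at entry p = 10–30%; 22% of varix-free placebo subjects develop varices; true ratio 0.60 (the protocol's primary-endpoint hazard ratio, borrowed); on-study detection equally complete for old and new varices. Let m be the share of prevalent cases scored as new, with the rest kept as non-events.

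**Dilution.** Prevalent cases contribute equally to both arms (ratio 1) and new cases contribute 0.60:

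- share of placebo events that are really prevalent: f = mp / [mp + 0.22(1 − p)]
- observed event ratio: R = f + 0.60(1 − f)

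| p | f, R if all misclassified (m = 1) | f, R if half misclassified (m = 0.5) |
|---|---|---|
| 0.10 | 0.100/0.298 = 0.34; 0.73 | 0.050/0.248 = 0.20; 0.68 |
| 0.20 | 0.200/0.376 = 0.53; 0.81 | 0.100/0.276 = 0.36; 0.74 |
| 0.30 | 0.300/0.454 = 0.66; 0.86 | 0.150/0.304 = 0.49; 0.80 |

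**No misclassification (m = 0).** All entry varices are known and kept as non-events. With a hazard ratio of 0.60, incidence on OCA among varix-free subjects is 1 − 0.78^0.60 = 0.1385. At p = 0.30 the ITT incidences are 0.7 × 0.22 = 0.154 (placebo) and 0.7 × 0.1385 = 0.097 (OCA). The cumulative-hazard ratio is ln(0.903)/ln(0.846) = 0.61; at p = 0.10 it is 0.60. The ratio hardly moves, but reported placebo incidence falls from 22% to about 15% at p = 0.30.

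**Direction for incidence.** Reported placebo incidence is 0.22 + p(m − 0.22). It is inflated only when m exceeds 0.22 and understated below that.

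**A second model.** An expected log-rank calculation assumed 175 subjects per arm, annual endoscopy for 7 years, a true hazard ratio of 0.60, placebo incidence of 3% or 5% per year, and every entry varix in examined subjects counted at the first on-study endoscopy (so m = 1). Ranges run over p = 10–30%.

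| Placebo incidence, subjects examined | Expected HR, whole ITT | Power, whole ITT | Power, varix-free set |
|---|---|---|---|
| 3% per year, all | 0.75–0.88 | 12–26% | 33–41% |
| 5% per year, all | 0.71–0.84 | 21–43% | 48–58% |
| 3% per year, half | 0.76–0.88 | 8–14% | 19–23% |
| 5% per year, half | 0.73–0.85 | 11–22% | 27–33% |

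The varix-free set gives about 0.61 throughout; the gap from 0.60 comes from the approximation. With no entry varices counted and only half the subjects examined, the whole-ITT estimate is 0.62–0.63. Never-examined subjects therefore add little dilution of their own.

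**The case against.** The strongest reply is that the protocol contains no rule making entry varices count as new. A reader might infer one from the ITT assignment, but Section 11.1.2 separates presence at baseline from later development. A subject with varices recorded at baseline would naturally be a non-event. That stands: for such subjects the hazard ratio is almost unaffected, and the reported incidence goes down.

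The exposed group is also narrower than the whole trial. Scheduled follow-up endoscopies in Sections 9.7.10 and 9.7.13 are limited to selected sites, as at Day 0. The clearest cases are subjects with no baseline examination who later have one as standard of care. The range for complete misclassification is therefore an upper bound.

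A reader might also infer that first examinations are often prompted by low platelets and so pick out those with old varices. The sentence beginning "Endoscopies should also be performed when platelet counts are" in Section 9.7.4 does not support this. It sits under the item on subsequent endoscopies, and no frequency is given.

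The endpoint is outside the testing hierarchy, so no error rate and no primary or key secondary result depends on it. That stands and limits the weight of the point.

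The argument that the SAP will settle it does not remove the point. Event derivation can be left to a SAP, but Section 13.1.5 itself fixes the ITT population without qualification. A SAP restricting to varix-free subjects would depart from that text.

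Nor does restriction break the randomized comparison. Baseline status is to be established at or before Day 0, and dosing starts on Day 1.

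**Conclusion.** The point holds in limited form. The stated risk set is wrong for an incident endpoint: varices in subjects without a baseline endoscopy can be scored as new, subjects with known varices stay at risk, and subjects never examined count as event-free. The documents do not support saying that entry varices are in general counted as new, that incidence is necessarily inflated, or that either arm is favoured.

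On the assumed inputs, a true ratio of 0.60 would appear as about 0.68–0.80 with half of the prevalent cases misclassified, at most 0.73–0.86 with all of them, and about 0.60–0.61 with none. The actual fraction cannot be derived from the protocol. Because the endpoint is descriptive and the expected bias is towards no effect, this is worth correcting but does not threaten the trial's main conclusions.

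**What to change.** In Section 13.1.5, define the population for this endpoint as randomized, dosed subjects whose endoscopy at Day 0, or within the preceding 12 months that Section 9.7.4 already allows, shows no varices. Time runs from Day 0 and the event is the first later endoscopy showing varices. Subjects without the event are censored at their last endoscopy rather than at last contact. Tabulate by arm the subjects with varices at baseline and those of unknown status, with their on-study findings.

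This takes a sentence or two in the protocol, carried into the SAP. It needs no new data and no change to who is examined. The price is a smaller denominator for one descriptive secondary endpoint. In the second model above, where all entry varices are counted as events, the restricted set has more power than the whole ITT population despite being smaller.
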